- Aim 2: Explore whether the effects of sPI are mediated by changes in sleep, depressive symptoms, activity circadian rhythms, melatonin and/or inflammatory markers.** Hypothesis 2a: The effects of sPI on CRF are mediated by changes in sleep quality. Hypothesis 2b: The effects of sPI on CRF are mediated by changes in depressive symptoms. Hypothesis 2c: The effects of sPI on CRF are mediated by changes in activity circadian rhythms (measured via actigraphy and melatonin rhythmicity). Hypothesis 2d: the effects of sPI on CRF are mediated by changes in inflammatory markers. **Aim 3: Determine the feasibility and acceptability of sPI, actigraphy, urine collection and monitoring of light exposure.** Hypothesis 3a: Initiating the sPI environment in patient hospital rooms during inpatient procedures (HSCT and initial chemotherapy regimen to treat MM and related oncological diseases) will be tolerable among MM-HSCT patients and medical professionals. Hypothesis 3b: sPI will be feasible as an inpatient treatment method to prevent common circadian rhythm-based side effects observed with HSCT and subsequent chemotherapy. Hypothesis 3c: sPI implementation inpatient hospital rooms will maximize potential patient benefit while minimizing deviation from normal lighting fixture end-user experience for both HSCT patients and medical professionals. Hypothesis 3d: Actigraphy collection among HSCT patients will be acceptable as an assessment method before, during, and after HSCT. Hypothesis 3e: Urine collection among HSCT patients will be tolerable as an assessment method before and during hospital visit for HSCT. Hypothesis 3f: Monitoring of light exposure via Daysimeter data among HSCT patients will be acceptable as an assessment method before and during HSCT.

2) Background

Debilitating fatigue – a persistent sense of exhaustion frequently associated with a number of serious medical conditions, including cancer – can interfere with mood, activities of daily living, treatment compliance. Such fatigue is often associated with sleep problems, depression, quality of life, and agitation. Unfortunately, currently available interventions for CRF are, at best, only modestly effective. Pharmacological agents have been studied for CRF, but there is insufficient evidence to recommend their use. Non-pharmacological interventions have shown clinical benefit, but they can be labor-intensive, expensive, and cumbersome for patients. A promising alternative is light therapy.

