- Eye Diseases which limit the ability of light to be processed (e.g., untreated cataracts, severe glaucoma, macular degeneration, blindness, pupil dilation problems or retina damage)
- Secondary cancer diagnosis within the last 5 years
- Severe sleep disorders (e.g., Narcolepsy)
- History of bipolar disorder or manic episodes (which is a contra-indication for light treatment)
- Severe psychological impairment (e.g., hospitalization for depressive episode in the past 12 months)
- Previous use of light therapy to alleviate fatigue or depressive symptoms

c) Number of Subjects

 Mount Sinai	Protocol Name:	Systematic Programmed Illumination of Hospital Rooms to Prevent/Reduce Cancer-Related Fatigue during Autologous Stem Cell Transplantation for Multiple Myeloma
	Principal Investigator:	[name]; [contact]
	Primary Contact Name/Contact Info:	[name], [contact], [contact]
	Date Revised:	8/15/2019
	Study Number:	IF# 2517160 HS# 15-00777 GCO#: 15-2009

For this feasibility study, we will recruit 60 participants drawn from the pool of upcoming HSCT admissions to treat MM at the MSH bone marrow transplant (BMT) clinic. Our previous research has demonstrated that at least 40% of this group either suffers from or will develop clinically significant fatigue related to cancer or its treatment.

d) Study Timelines

Total participation in this study is 16-18 weeks, and may vary by hospital admission, length of hospital stay, and expediency of returning study related materials.

Endpoints

The primary endpoints in the proposed study are: 1) Fatigue as measured by a simple Graphic Rating Scale, Multidimensional Fatigue FACIT Fatigue Scale, and The Pittsburgh Sleep Quality Index; 3) Depression as measured by the CES-D; 4) Quality of Life measured by the SF-36 scale; 5) Sleep/wake activity measured using an actigraph; and 7) Biological variables melatonin and inflammatory markers (i.e., IL-1ra, IL-6, MCP-1/CCL2, MIP-1a/CCL3, sTNFr1, sIL-6R, CRP) as obtained via urine and blood analysis.

The secondary endpoints include: 1) the amount of light received by the patient as measured by the Daysimeter; 2) treatment satisfaction using the FACIT-TS-G scale, and 3) Psychological moderators (e.g., emotions, symptom burden) that may affect for whom the treatment is effective.

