Please see the Data Safety and Monitoring Plan in section 5h for procedures taken to lessen the probability or magnitude of risks.

Data about subjects will be collected from medical charts, urine samples, blood samples, questionnaires that the participants will fill out, and output from the equipment (i.e., Actigraph and Daysimeter data).

 Mount Sinai	Protocol Name:	Systematic Programmed Illumination of Hospital Rooms to Prevent/Reduce Cancer-Related Fatigue during Autologous Stem Cell Transplantation for Multiple Myeloma
	Principal Investigator:	[name]; [contact]
	Primary Contact Name/Contact Info:	[name], [contact], [contact]
	Date Revised:	8/15/2019
	Study Number:	IF# 2517160 HS# 15-00777 GCO#: 15-2009

If there are any adverse events during the screening and consent process, the study participants will have the option to be put in contact with the a licensed clinical psychologist. The suicidality protocol will be in place throughout the entire study. It will be in the judgment of the consenting professional and/or as per medical record to determine if a patient may have severe psychopathology or cognitive impairment likely to interfere with the participation or completion of the protocol or ability to provide meaningful information. In this case, professional will decide not to include potential participant in the study.

The following questionnaires will be completed during the study:

Background Measures:

- Background Information Questionnaire – Socio-demographic data regarding gender, age, ethnicity, religion, income, marital status, and employment status will be gathered during the screening assessment and any changes in information will be gathered at the follow-up assessments. We will assess co-morbid medical conditions and current prescription sleep-related and non-sleep-related medications.
- Chronotype (MEQ) – We will collect data on baseline circadian predispositions using the Morningness-Eveningness Questionnaire, a 19-item self-rated survey designed to measure whether a person’s peak alertness is in the morning or the evening. Takes approximately 2 minutes to complete.

Credibility Measures:

- Credibility/Expectancy Questionnaire – This questionnaire will ask whether the patient feels the light box is a useful and/or effective treatment for CRF.

Sleep and Fatigue Measures:

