alertness are indicative of high PA, whilst lethargy and sadness characterize low PA. Both the PA and NA have decent Test-retest reliability ($r=0.68$ and $r=0.71$ respectively) and decent Internal Consistency (Cronbach's $\alpha = 0.87$).

Symptom Measures:

- **Brief Symptoms Inventory-18 (BSI-18)** - BSI-18 is one an integrated series of instruments designed to measure psychological distress. A more concise version of the 53 item BSI, the BSI-18 boasts 18 items and, according to its authors, this inventory presents satisfactory reliability indexes, both for the dimensions (ranging from .74 to .84) and the general distress index (.89). It has decent Test-retest Reliability ($r=0.76$) and good Internal Consistency (Cronbach's $\alpha = 0.89$).

Medical tracking form - Medical data will be gathered through medical chart review and interview including comorbid and excluded medical conditions, medical information related to transplant, current prescription sleep-related and non-sleep-related medications, history of treatment with light therapy, and remaining exclusion criteria. During the final timepoint, research coordinators will check the participant's medical chart using the medical tracking form and enter updated relevant health information into a password protected file.

f) Specimen Banking

Urine Samples –

All 60 participants will be assessed using biological measures (via urine samples) at two points. Samples will be collected once during baseline 1 before their transplant admission and once during inpatient treatment (on Day Three of engraftment)..

Outpatient urinary samples will be collected at home by the participant, according to the provided timetable. Exact times will be noted on the samples in case of any variance in sample timing. Participants will be instructed to collect any void after 11pm up to 1st AM void overnight during the 72-hour span of wearing the actigraph and daysimeter at baseline, and then during hospitalization prior to discharge. Urinary sample containers will be provided by the study team. Collection time of samples will be written on the outside of the containers by participants. Samples will be refrigerated and mailed directly to RPI LRC Biomarker Lab for analysis using a pre-paid shipping label provided by RPI.

Biological samples collected in the hospital will be gathered according to regular BMT procedures by a registered nurse or physician, and processed as with at-home collections.

Blood samples –

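### Only prescription medications must be recorded, so non-prescription melatonin may enter the urinary melatonin outcome and the Hypothesis 2c mediator without being recorded

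*Combined protocol and SAP*

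**What the plan says.** **Role of melatonin.** The endpoint list under section 5d puts "Biological variables melatonin and inflammatory markers" among the primary endpoints. The Data Analysis text in section 5g places melatonin among the secondary outcomes and tags it exploratory. Hypothesis 2c (section 1) proposes that the effect on fatigue is "mediated by changes in activity circadian rhythms (measured via actigraphy and melatonin rhythmicity").

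**Collection.** Section 5f gives two urine timepoints: baseline 1, at home, and day three of engraftment, in hospital. Participants collect voids from 11pm to the first morning void. The instructions cover timing and handling, and the container carries the collection time.

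**Medication capture.** It is described twice in section 5e. For the Background Information Questionnaire: "We will assess co-morbid medical conditions and current prescription sleep-related and non-sleep-related medications". For the medical tracking form, the items include "medical information related to transplant, current prescription sleep-related and non-sleep-related medications, history of treatment with light therapy, and remaining exclusion criteria". That form's source is wider than the chart: "Medical data will be gathered through medical chart review and interview including comorbid and excluded medical conditions".

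**Other places where intake could be caught.** The exclusions in section 5b include severe sleep disorders and "Previous use of light therapy to alleviate fatigue or depressive symptoms", but do not mention melatonin, supplements or sleep aids. The sleep log covers bed and rise times, device removal and periods of sitting still. Section 5g says that urine is analysed under the laboratory's own protocol, which is not part of the document.

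**Confounders.** Section 5g compares the arms at baseline on several variables, medications among them, and carries any that differ into the models as covariates.

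**The concern.** A urine measure of the body's own melatonin can be interpreted only if one knows whether the participant also swallowed some. I assume that melatonin can be bought without a prescription where the trial recruits and that a bedtime dose reaches urine collected overnight; the documents address neither point. On those assumptions, a site following the plan to the letter may enrol a user and collect the sample with nothing on a study form to show it.

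The outcome is fragile because it has only two timepoints. A participant who takes melatonin on one collection night and not the other has a change score that largely reflects the product. That change score is what the Hypothesis 2c mediator would use. The covariate step in section 5g does not help: it uses baseline variables, and it cannot use a product that was never recorded.

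Section 2 gives monitoring of entrainment through urinary melatonin as one reason for choosing this population, and section 5e makes the feasibility of studying biological mediators an aim. Samples of uncertain meaning weaken both.

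**Working it through.** The plan states no figure that depends on this point, so there is nothing to reproduce. The check has two parts.

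**1. Can the described forms capture it?**

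| Record | Content described | Non-prescription melatonin required? |
|---|---|---|
| Eligibility (5b) | Sleep disorders, prior light therapy, others | No |
| Background questionnaire (5e) | Prescription medications | No |
| Medical tracking form (5e) | Prescription medications, from chart and interview | No, though it might be noted |
| Sleep log (5e) | Bed times, device removal, sitting still | No |
| Urine instructions (5f) | Timing and handling | No |
| Laboratory (5g) | Refers to a protocol not shown | Cannot be seen |

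If the word prescription is read as qualifying only the sleep-related drugs, a non-prescription product taken for sleep is still not covered.

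**2. How large could the effect be?** The only inputs from the documents are 60 participants, 30 per arm and alpha 0.05. The share of users *q* and the rise in a user's value, *k* standard deviations (SD), are assumptions.

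*Chance of at least one user among 60:* 1 − (1 − q)^60. For q = 2%, 5% and 10% this is 0.70, 0.95 and 0.998, with 1.2, 3 and 6 users expected.

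*Chance imbalance:* one extra user in an arm of 30 shifts that arm's mean by k/30, which is 0.10 SD for k = 3 and 0.33 SD for k = 10. At q = 5%, the difference in user counts between arms has SD √(2 × 30 × 0.05 × 0.95) = √2.85 = 1.69. A one-SD imbalance therefore shifts the contrast by 1.69 × 0.10 = 0.17 SD to 1.69 × 0.333 = 0.56 SD.

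*Noise, with equal use in both arms:* the SD grows by s = √(1 + q(1 − q)k²). An effect that has 80% power without users is d = (1.960 + 0.842) × √(2/30) = 0.72 SD. Its power becomes Φ(d / (s√(2/30)) − 1.96).

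| q | k | s | Power |
|---|---|---|---|
| 2% | 3 | 1.08 | 0.73 |
| 2% | 10 | 1.72 | 0.37 |
| 5% | 3 | 1.19 | 0.65 |
| 5% | 10 | 2.40 | 0.21 |
| 10% | 3 | 1.35 | 0.55 |
| 10% | 10 | 3.16 | 0.14 |

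*On the log scale:* assume a coefficient of variation of 0.5 and a rise of 10- to 100-fold. The log variance is ln(1 + 0.5²) + q(1 − q)(ln k)², where k is now the fold rise, and 0.223 without users. For q = 5% and 10-fold it is 0.223 + 0.0475 × 5.302 = 0.475, an SD ratio of √(0.475/0.223) = 1.46. For q = 10% and 100-fold it is 0.223 + 0.09 × 21.208 = 2.132, a ratio of 3.09. A log transformation reduces the problem but does not remove it.

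**Direction.** Light is given only during the hospital stay, so melatonin use at the baseline 1 collection cannot be a consequence of it. At baseline, randomisation leaves noise and chance imbalance. Only use on the inpatient collection night could depend on arm.

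**The case against.** **A user need not go unnoticed.** The tracking form draws on chart review and interview, and its list is introduced by the word including, so it may not be complete. Melatonin ordered in hospital could appear in the chart. The questionnaires themselves and the laboratory protocol are not in the document. A reader might infer that every user would go undetected; the document does not support that. It supports the narrower statement that capture is not required.

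**Large values might be obvious.** With a coefficient of variation of 0.5, a 10-fold value lies (10 − 1)/0.5 = 18 SDs above the mean. That would stand out in descriptive statistics. But no rule says what to do with it, a decision made then would follow sight of the data, and a smaller rise might not stand out.

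**Bias between arms is not shown.** A reader might infer that dim-light participants would sleep worse and take more melatonin, hiding or reversing a light effect. Nothing in the documents gives use by arm, and the calculations above do not test that scenario. It is possible only for the inpatient sample, chiefly through self-supplied use.

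**The outcome is exploratory.** Section 5g says so, Aim 2 sets out to explore mediation, and section 5c calls this a feasibility study. This limits the weight of the point. It does not remove it, because the endpoint list under section 5d still counts melatonin as primary.

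**Dropping affected samples has its own fault.** If inpatient use depends on arm, excluding those samples selects on something that happened after randomisation. This stands, and it shapes the fix.

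**Conclusion.** The gap is real but limited. As written, the plan does not require anyone to record non-prescription melatonin or sleep aids, so exogenous melatonin may enter a two-timepoint outcome and the Hypothesis 2c mediator without a record. The main harms are noise, chance imbalance and distorted baseline-to-inpatient change scores.

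The size cannot be taken from the documents. The illustrations rest wholly on assumed prevalence and assumed rises, and show only that a few users among 60 could matter.

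Two further inferences are not supported. The fatigue outcome is not threatened directly, since it is not measured from urine. Nor is the absence of a melatonin exclusion criterion itself the defect: what is needed is a record of use, not a restriction on it. The point is a cheap improvement to data capture.

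**What to change.** 1. In both section 5e descriptions, widen the medication item to *current prescription and non-prescription (including melatonin)*.
2. At each urine collection, home and inpatient, record any melatonin or sleep aid taken and the time. The sleep log could carry this at home; the document describes no inpatient collection record, so a place for the item must be named.
3. In the Data Analysis text, state that use will be reported by arm and timepoint, that affected samples will be flagged, and that the melatonin and Hypothesis 2c analyses will be run with and without flagged samples. Note that omitting inpatient samples conditions on a post-randomisation variable.

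The cost is a few form items and one extra analysis, with fewer samples in the analysis that omits flagged ones. Patient care does not change. If forms are already in use, the handling rule can still be fixed before analysis, but intake that was not recorded will be hard to recover.

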	Protocol Name:	Systematic Programmed Illumination of Hospital Rooms to Prevent/Reduce Cancer-Related Fatigue during Autologous Stem Cell Transplantation for Multiple Myeloma
	Principal Investigator:	[name]; [contact]
	Primary Contact Name/Contact Info:	[name], [contact], [contact]
	Date Revised:	8/15/2019
	Study Number:	IF# 2517160 HS# 15-00777 GCO#: 15-2009

Research related blood draws will be performed at four time points corresponding with routine clinical blood draws: First blood draw upon admission to the hospital, at the third day of engraftment (T3e, at the clinical visit about one month post-transplant (T4) and at the clinical visit about three months post-transplant (T5). Blood will be collected at MSH by a licensed phlebotomist. At each time point 16.7mL (approximately 3.5 teaspoons) will be collected in red top SST tubes, yellow top ACD tubes, and blue top Tempus tubes, delivered within 30 minutes, and processed immediately in the laboratories of Mount Sinai's Human Immune Monitoring Core Shared Resource Facility according to established blood processing protocols.

g) Data Management and Confidentiality

All data obtained will be placed into individual research participant folders and stored in a locked file cabinet in the department of Oncological Sciences. Only study personnel will have access to this file cabinet. All folders and data pertaining to individual subjects will be identified only by a code number and only the PI ([name]) and Co-investigator ([name]) the research coordinators will have access to electronic file that links the numbers to patient identities. Upon completion of the study, the file that links patients to the codes will be deleted.

Data sent between RPI, Mount Sinai, and the participants will be shipped via UPS. Patient names and dates of birth will not be included in mailed data to protect patient privacy. Mailed data will only be identified with study-ID numbers. RPI will be assessing melatonin levels, and will not receive any protected health information (PHI) other than the results of the biological assessments as well as assessments taken over the course of the study.

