Data from any web-based assessment tools will be accessible to research study team using password protection and will only be identified by participant ID number. Paper files and printouts of assessment scores will be kept in a locked cabinet with access only by authorized project research staff. The use of email will be in accordance with MSH policy (i.e. secure email, obtaining consent from subject to send email, etc.).

Urine and blood samples will be marked only by study ID number and no other identifying information.

Data Analysis:

Descriptive statistics will be calculated both for the entire group and separately for each treatment group. T-tests and Fisher's exact tests will be used to assess group differences at baseline for possible confounders (i.e., demographic variables, clinical characteristics, and medications). Any variables showing differences between the two groups will be used as covariates in subsequent analyses. Since there is no known seasonality effect to measures of fatigue or to measures of sleep, which are our main outcome measures, seasonality will not be controlled in these analyses. For the primary outcome (Fatigue), the secondary outcomes (Depression, Sleep, Circadian Activity Rhythms, melatonin (exploratory), and Quality

	Protocol Name:	Systematic Programmed Illumination of Hospital Rooms to Prevent/Reduce Cancer-Related Fatigue during Autologous Stem Cell Transplantation for Multiple Myeloma
	Principal Investigator:	[name]; [contact]
	Primary Contact Name/Contact Info:	[name], [contact], [contact]
	Date Revised:	8/15/2019
	Study Number:	IF# 2517160 HS# 15-00777 GCO#: 15-2009

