of Life), hierarchical random effects linear mixed models will be employed for Aims 1 and 2 using MIXED with repeated measures. Besides time (linear and possibly quadratic trends to allow for possible nonlinear trends), any covariates identified in the preliminary analyses and intervention group will be assessed in a fixed effects model. Each model will also include a random intercept. Post-hoc comparisons will be Tukey-adjusted. Since there are multiple secondary outcomes, the p-values will be Sidak adjusted for correlated multiple comparisons. Any variations in length of hospital stay (i.e., length of intervention) will be used as a covariate in all analyses. This is highly unexpected since 90% of ASCT patients are hospitalized for 14 days. In the Analysis of Aim 2, we will establish that the treatment is a significant predictor of the primary outcome (CRF) as well as the hypothesized mediators. Next, we will first examine the role of each of the mediators of the effects of sPI on CRF by introducing each individually into the equation which contains the time variable, the treatment main effect, and the time by treatment interaction. Each mediator which is a significant predictor of CRF in this equation will then be combined with any other significant mediating predictor of CRF into a single equation. We predict the introduction of each significant mediator will result in the decrease in the significance of the time by treatment interaction effect on CRF. However, the more important test of the mediating role by any variable will depend on the statistical significance of the indirect path from treatment to mediator and from mediator to the outcome. Following procedures suggested by Shrout and Bolger (2002), 1000 bootstrap samples will be employed to determine the significance of each indirect path.⁵⁰ **Power:** It is difficult to discuss power for **Aim 1** and **Aim 2** since there is no directly relevant past research. As a consequence, one of the goals of this project is to obtain estimates of the effect sizes that will eventuate from our proposed analyses. Although unknown at the moment, these effect sizes can guide decisions regarding sample sizes for a larger scale grant. In the interim, there are three lines of research that may provide some guidance. The first involves the work of [name], who investigated the effects of light treatment on fatigue experienced by women undergoing chemotherapy for breast cancer.⁹ Using her results, we calculated power for a repeated measures design with an autoregressive lag 1 structure and autocorrelations ranging from 0.40 to 0.60. With alpha equal to 0.05 and a sample size of 30 patients per group, power ranged between 0.96 and 0.98. We followed a similar approach using [name]'s results but focusing only on MM survivors of ASCT.¹⁰ In this case, power was 0.99 for autocorrelations ranging between 0.40 and 0.60. However, the latter results must be treated cautiously because these calculations were based on a very small sample (N = 17 survivors). Using the same small sample, our repeated measures analysis of depression indicated that the time by treatment condition interaction was marginally significant (p = 0.0568). The F-ratio for this interaction yielded an eta coefficient of 0.48 which would be considered moderately strong following Cohen's criteria.⁴⁹ We hypothesize that the interaction effect would have been significant had the sample size been larger as is being proposed in this study (N = 60). Because of the very small survivors sample and the variability of our indicator of circadian activity rhythms (the f-statistic), the Mixed program did not converge and it was not possible to obtain a power estimate for this outcome. The third line of research that is germane to power in the proposed pilot study was conducted by Sim and Lewis who applied the UCL approach and found that a pilot sample of n => 55 would minimize the overall sample size for small to medium standardized effect sizes (0.2-0.6).

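### Melatonin is sampled twice but assigned to a time-trend model with no baseline covariate, and the blood markers lack baseline adjustment too; a baseline-adjusted analysis would be more precise with no new data

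*Combined protocol and SAP*

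**What the plan says.** **Sampling.** Section 5(f), Urine Samples: "All 60 participants will be assessed using biological measures (via urine samples) at two points", namely baseline 1 and the third day of engraftment. Section 5(e) also gives two urine time points. One sentence in section 2 (Background) speaks of urine before, during and after transplant, which suggests a third. Section 5(f), Blood samples: "Research related blood draws will be performed at four time points corresponding with routine clinical blood draws", namely admission, engraftment day 3, and about one and three months after transplant.

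**Model.** For fatigue and for "the secondary outcomes (Depression, Sleep, Circadian Activity Rhythms, melatonin (exploratory"), plus quality of life, section 5(g) states that "hierarchical random effects linear mixed models will be employed for Aims 1 and 2 using MIXED with repeated measures". The fixed effects listed are time (linear, possibly quadratic), intervention group and covariates, with a random intercept. The covariates are those demographic, clinical or medication variables that differ between arms at baseline, plus length of stay. The baseline value of the outcome is not among them. No measurement scale or transformation is given for any assay.

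**Inflammatory markers.** The Endpoints text in section 5(d) lists melatonin and seven inflammatory markers under the primary endpoints. The outcome list in section 5(g) has melatonin as secondary and exploratory, and omits the inflammatory markers. They enter the analysis through Aim 2, where Hypothesis 2d makes them mediators and section 5(g) plans to show that treatment predicts each mediator.

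**The concern.** One generic model is written for outcomes with very different sampling schedules. It suits a questionnaire collected many times. For a urine measure collected once before and once during treatment, it leaves a single useful contrast and does not use the baseline value in the most efficient way. The blood markers have four time points, so a trend can be fitted, but they too have no baseline adjustment and no marker-specific model.

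At stake is the precision of the treatment-to-mediator path in Aim 2, and of the effect sizes that the study is meant to supply for a larger trial: "Although unknown at the moment, these effect sizes can guide decisions regarding sample sizes for a larger scale grant". Leaving scale and adjustment open for eight biomarkers also leaves those choices to be made after the data are seen.

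**Working it through.** **The plan's own figure.** No power is given for melatonin or any blood marker. The nearest statement concerns fatigue: "With alpha equal to 0.05 and a sample size of 30 patients per group, power ranged between 0.96 and 0.98", for a "repeated measures design with an autoregressive lag 1 structure and autocorrelations ranging from 0.40 to 0.60". It cannot be reproduced, because the effect size, SD and number of time points are not stated. Solved backwards for a single two-group contrast (two-sided 0.05 assumed), d = (1.96 + z) × √(2/30) gives 0.96 for 96% power and 1.04 for 98%. It has no bearing on the assays.

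**What the model becomes with two samples.** Take unit SD at both times, correlation r, and an arm effect d at the second sample only.

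- Quadratic time: two points determine a line, so the term cannot be estimated.
- Arm-by-time interaction: equals the difference in mean change. Effect d, variance 2(1−r).
- Arm main effect without interaction (the model sentence read literally): equals the difference in the mean of the two samples. Effect d/2, variance (1+r)/2.
- Analysis of covariance (ANCOVA) on baseline: effect d, variance 1−r².

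ANCOVA relative to change: (1−r²)/(2(1−r)) = (1+r)/2, which is 0.65, 0.75 and 0.85 at r = 0.3, 0.5 and 0.7.

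The direction does not need equal variances. With SDs s0 and s1, the change-score variance minus the ANCOVA variance is s0² + s1² − 2r·s0·s1 − s1²(1−r²) = (s0 − r·s1)², which is never negative.

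**Power, baseline adjustment alone.** Assumed, not in the documents: d = 0.6, r = 0.3 to 0.7, two-sided 0.05, no Sidak adjustment. 30 per arm is from the plan. Power = Φ(effect/SD × √15 − 1.96).

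| Analysis | r = 0.3 | r = 0.5 | r = 0.7 |
|---|---|---|---|
| Arm main effect, no interaction | 30% | 27% | 24% |
| Change score | 50% | 64% | 85% |
| ANCOVA on baseline | 68% | 77% | 90% |

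Worked case at r = 0.3: change, 0.6/√1.4 × √15 = 1.96, so Φ(0.00) = 50%; ANCOVA, 0.6/√0.91 × √15 = 2.44, so Φ(0.48) = 68%.

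A low r is plausible. Urine is taken at baseline 1, and section 5(e) allows baseline 1 to fall more than two months before transplant.

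**Adding the log scale.** Simulated log-normal data, 10,000 runs per cell, log-scale d = 0.6. The log SD is √ln(1+CV²), so the arm ratio runs from 1.19 (CV 0.3) to 1.92 (CV 1.5). Power at r = 0.3 / 0.5 / 0.7:

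| Per arm | Raw CV | Raw change | Log ANCOVA |
|---|---|---|---|
| 30 | 0.3 | 50/64/84% | 66/75/89% |
| 30 | 0.5 | 48/61/81% | 67/75/89% |
| 30 | 1.0 | 41/51/69% | 66/74/89% |
| 30 | 1.5 | 34/43/59% | 66/75/89% |
| 21 | 0.3 | 37/48/69% | 50/58/75% |
| 21 | 1.0 | 30/38/54% | 50/58/74% |
| 21 | 1.5 | 25/31/44% | 49/57/75% |

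The 21 per arm comes from the 71% retention expected in section 2: 60 × 0.71 = 42.6. At 30 per arm the total gain runs from 5 points (CV 0.3, r = 0.7: 84 to 89) to 32 points (CV 1.5, r = 0.3: 34 to 66). On change scores, the log step alone adds about 0 points at CV 0.3, 1–3 at CV 0.5, 8–15 at CV 1.0 and 14–26 at CV 1.5. With no true effect, all analyses rejected in about 4–5% of runs.

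**The case against.** The strongest reply has four parts.

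1. *Small consequence.* This is a feasibility study ("For this feasibility study, we will recruit 60 participants drawn from the pool of upcoming HSCT admissions"), melatonin is labelled exploratory, and power for exploratory assays decides nothing. That limits the weight of the point. It does not remove it, because estimating effect sizes is a declared goal and the better analysis uses data already collected.
2. *The quadratic term is optional.* It would simply be dropped for melatonin. Agreed; the term alone is a minor matter. What remains after dropping it is still a change score or a diluted main effect.
3. *The power gains are built in.* Log-normal data with a multiplicative effect favour a log analysis, and the documents give no SD, skewness, correlation or effect size for any assay. This stands in full for the log scale. It does not touch the (1+r)/2 result, which needs no skewness.
4. *The blood markers are covered.* Mixed models are named for Aims 1 and 2, and treatment is to be tested as a predictor of each mediator. This stands. What is missing is the marker-specific detail, the baseline adjustment and a consistent endpoint status.

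A reader might also worry that blood is drawn at unrecorded clock times, so that a shift in rhythm could pass for a change in level. The documents do not make this a defect of the comparison. Both randomised arms follow the same routine draws, and a common clock-time covariate could not separate phase from level if one arm had shifted.

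**Conclusion.** The point holds as one of precision. For melatonin, the stated model yields a change-score test, or a weaker averaged test if no interaction is fitted, while an available baseline value goes unused as a covariate. Baseline adjustment alone reduces the variance to 0.65–0.85 of the change score's for assumed r of 0.3–0.7, under equal variances. At an assumed d of 0.6 and 30 per arm that is worth roughly 5 to 18 power points. With the log scale added, the total is about 5 to 32 points under the assumed ranges, the upper end only with strong skew. The Sidak adjustment would lower every power figure.

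Four stronger readings are not supported:

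- That the plan chooses the raw scale: it is silent on scale.
- That the blood markers have no analysis: Aim 2 provides a generic one.
- That the evidence for Aim 1 rests on these assays: Hypothesis 1a assesses circadian rhythms by actigraphy and names neither melatonin nor blood markers.
- That real effects will be missed, or that a large amount of power is certainly lost: this depends on figures the documents do not give, and the planned test keeps its type I error near 5%.

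**What to change.** - **Melatonin:** analyse the engraftment day 3 value by ANCOVA with baseline melatonin as covariate and no trend terms, or by an equivalent constrained longitudinal model that keeps patients with only one sample. Define the single melatonin summary per occasion, since several overnight voids may be collected within the 72-hour span.
- **Blood markers:** analyse each at engraftment day 3 and at the two follow-up visits, with its admission value as covariate. Seven markers at three times give 21 comparisons, so state whether these are exploratory estimates or fall under a multiplicity rule.
- **Scale:** prespecify the log scale for these assays, on the stated assumption of right skew, and report arm ratios with 95% intervals.
- **Aim 2:** use the same models for the treatment-to-mediator path.
- **Consistency:** reconcile Endpoints (section 5d) with Data Analysis (section 5g) on the status of melatonin and the inflammatory markers, and section 2 with section 5(f) on the number of urine collections.
- **Optional:** enter blood draw time as a covariate for noise, without claiming that it separates phase from level.

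The cost is SAP wording; the core changes need no new data. Results become ratios rather than assay units, and plain ANCOVA drops patients who lack either sample, which matters at 71% retention and is the reason to offer the longitudinal form.
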